4.4.3. Substance Use Assessments

Urine Drug Screen (UDS): Urine drug screens will be performed once a month at the OTP as part of usual care for each participant during the study. The monthly urine specimens collected at the OTP are screened via enzyme immunoassay (EIA) and liquid chromatography-mass spectrometry (LCMS) is used for result confirmation to test for the following drugs: opiates, oxycodone, fentanyl, barbiturates, benzodiazepines, cocaine, amphetamine, methamphetamine, marijuana (THC), methadone, and ecstasy (MDMA). Monthly UDS data collected at the OTP will be documented into the UDS CRF at each monthly study visit via medical record review. Any UDS results demonstrating ongoing opioid use or other illicit/nonmedical substance use (e.g., cocaine) will be reported to the site PI to determine whether the participant should continue in the study.

Timeline Followback (TLFB): The Timeline Followback (TLFB) assessment will be used to collect self-reported information on substance and alcohol use over a 30-day look-back period, for which it has shown high test-retest reliability and validity (Sobell and Sobell 1992; Sobell and Sobell 2000). Participants will be asked to report daily substance and alcohol use since the previous TLFB assessment at the Intake/Baseline Visit and each monthly research visit. If a participant discontinues study participation early, the TLFB assessment also will be administered at the Early Termination Visit.

4.4.4. Methadone Treatment Assessments

Methadone Visit Checklist: This form will be completed by the study pharmacists to document all study medication administered and dispensed at each Pharmacy visit, including the daily prescribed dose of methadone and the lot number and expiration date of administered/dispensed medication. This form also will be used to document pharmacist-provided care, such as (1) performing methadone prescription reconciliation, (2) providing patient education (e.g., safe storage, medication side effects); (3) checking and recording the patient's controlled medications prescription status using the NC Controlled Substances Reporting System [CSRS]; (4) monitoring and recording safety related events/concerns and communicating with the OTP medical physician or staff promptly regarding the event/concern; and (5) administering one methadone dose at the pharmacy and dispensing methadone according to the prescription of the OTP physician and applicable federal/state guideline for methadone treatment for opioid use disorder. Communications between the study pharmacist and the OTP medical physician or staff will be documented on the form, such as reasons for changes in methadone doses and/or take-home schedule.

Methadone Call-Back: The OTP medical staff (e.g., nurse) will implement the call back procedure. This form will collect the written results provided from the OTP medical staff to document the outcome of each random methadone call-back visit during the study period (i.e., at least once for every study participant after the first methadone dispensing by study pharmacist(s)), including the amount of used and unused medication returned. Failure to successfully complete call back result in termination from the study and return of the participant to the OTP for further assessment and ongoing treatment. This Methadone Call-Back form will include questions assessing whether a random methadone call-back visit is completed, its date, and the outcome of the call back (e.g., brought back all doses or not). The OTP staff is required to sign and date the form that a call back was done and its results (e.g., brought back all doses or not).

Treatment Satisfaction Survey: Participants, pharmacists and methadone treatment physicians will be asked to rate their overall satisfaction with the quality of the treatment (modified from Harland et al., 2015). Participant

satisfaction with treatment will be recorded on the Treatment Satisfaction Survey (based on a 5-point Likert scale: 0 = very dissatisfied, to 5 = very satisfied) that is completed by study participants at each study visit (1-4), including the Early Termination Visit (if participant discontinues study participation early). Pharmacists and physicians will also be asked to complete the Treatment Satisfaction Survey once per month, beginning the month of the first participant, first visit (FPFV; Visit 1) at their paired site and ending the month of the last participant, last visit (LPLV) at their paired site.

End of Methadone Medication Form: This form tracks the participant's status with regard to the study intervention/medication. It will be completed at the pharmacy at the Early Termination Visit (if participant discontinues study participation early), or at the LAST visit at the pharmacy for methadone administration and dispensing, which will occur about 3 months after the first pharmacy visit. Remote/virtual interviews by phone or the Duke-approved teleconferencing platform for research may be used to collect study assessments for participants who discontinue study participation early and are unable to return for Early Termination Visit during the specified time period.

Methadone Treatment Education Feedback Questionnaire: We will collect the opinions of pharmacists and OTP physicians about the clarity and utility of the study training materials, as well as any lack of useful information from the training. The questionnaire will consist of specific questions on the training modules to be rated on a 5-point Likert Scale of satisfaction, and will be filled out at the end of the training phase and once all participants have completed the study. The results will be used to structure training materials for a subsequent clinical trial.

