**Protocol Date: February 2, 2021
Version 6.0**

**A pilot study to permit Opioid Treatment Program physicians
to prescribe methadone through community pharmacies for
their stable methadone patients
(OTP-Pharmacy Care)**

Principal Investigator (PI):
[name], RN, MA
Duke University School of Medicine

Site PI:
[name]
Morse Clinics

Co-Investigator:
[name]
Friends Research Institute

Project Manager (PM):
[name]
Duke University School of Medicine

1. Abstract

The overall objective of this pilot implementation study will focus on exploring a collaborative care model aimed at increasing access to methadone maintenance treatment (MMT). The study aims are to determine the feasibility, acceptability, and satisfaction of patients and opioid treatment program (OTP) providers (e.g., medical staff, nurses, and counselors) and pharmacists with community pharmacy administration and dispensing of methadone for patients with opioid use disorder (OUD).

Approximately 20 adults, aged 18 or older, who have been stabilized on MMT long-term for OUD and who receive between 6- and 13-days of methadone take-home doses will be enrolled in the study. Participants will be recruited from 1-2 OTPs. Morse Clinic of North Raleigh (Raleigh, NC) will serve as the primary OTP site for the study; Morse Clinic of Zebulon (Zebulon, NC) will serve as a backup OTP site for this study. Health Park Pharmacy (Raleigh, NC) will be the study pharmacy site.

Given the pilot study nature and the focus on implementation issues, this study will use a non-randomized, prospective, single group design. After the intake study assessment (baseline), the administration and dispensing of participants' take-home methadone doses will be transferred from the OTP to the pharmacy for 3 months under the supervision of methadone prescriber (medical provider). Each participant will be assessed monthly for 3 months (at 1, 2, and 3 months following intake/baseline) to explore the feasibility of transferring their methadone administration and dispensing to the select community pharmacy.

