- a) Calculate the rate of recruitment, defined as the number of participants enrolled in the study out of the number of MMT patients who are potentially eligible and approached for participation. The average monthly rate of participants starting pharmacy-based methadone dispensing for OUD among enrolled participants will also be calculated. The number of potential participants pre-screened and the reasons for pre-screen failure and screen failure will also be evaluated.
- b) Calculate the adherence to methadone treatment defined as (1) the proportion of methadone take-home doses dispensed at the pharmacy out of the total number of take home doses prescribed and (2) the proportion of successful scheduled methadone dose call-back with no signs of methadone diversion.
- c) Examine retention in treatment, as determined by the proportion of participants who remain in treatment at the pharmacy during the 3-month follow-up phase.

- d) Examine the proportion of positive urine drug screens (UDS) over the study duration.
- e) Examine the number of days of self-reported substance use (alcohol intoxication, and other drugs) as collected on Timeline Followback (TLFB) over the study duration (Sobell, 1992; Sobell & Sobell, 2000).
- f) Determine indicators of participant satisfaction with treatment delivery measured using the Treatment Satisfaction Survey (adapted from Harland et al., 2005) obtained at each assessment; proportion of visits in which raters are satisfied (score of 4 on a Likert Scale of 1-5) or very satisfied (score of 5 on a Likert Scale of 1-5).
- g) Determine pharmacist and physician satisfaction with treatment delivery measured using the Treatment Satisfaction Survey at follow-up assessment, and a proportion of physician and pharmacist ratings of satisfied or very satisfied.
- h) Examine participant safety, as measured by: (1) Any fatal or non-fatal substance-related overdose measured by medical examiner record or self-report, respectively; and (2) Any substance-related emergency department (ED) visit or hospitalization, measured by self-report.

3. Background and rationale

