Participants will complete three follow-up assessments at 1-month, 2-months, and 3-months following the baseline visit. These follow-up assessments will be completed either in-person between the participant and research staff or remotely via phone or a Duke-approved teleconferencing platform for research. Assessments will focus on collecting clinical and safety information since the previous assessment, including substance use data via urine toxicology samples and self-report using the timeline followback (TLFB) assessment, compliance with psychosocial interventions, medication side effects or other safety events, and suicidality risk evaluation. The full list of assessments to be administered is included below (**Table 1**). Based on the convenience of the patient's time and methadone take-home schedule, monthly research assessment may be scheduled to occur on a day that take-home doses are scheduled to be dispensed. Completion of the intake/baseline assessments will take approximately 45-60 minutes. Follow-up research interviews will be briefer, about 30 minutes in duration.

Using the guidance from the pharmacy practice's collaborative practice agreements (CPAs), the role and responsibilities of study pharmacists (Health Park Pharmacy, Raleigh, NC) and study OTP prescriber/physician ([name]), including communication procedures, will be specified by an Operational Care Agreement (OCA) and signed by study pharmacists and [name]. Throughout the study, participants will continue to receive their usual care at the OTP (e.g., counseling, methadone provider

oversight of dose orders, urine drug screen) and participants will return to their OTP at the end of the study (i.e., 3 months after baseline). The last monthly study assessment (3 months after baseline) will occur remotely (via phone or a Duke-approved teleconferencing platform), at the OTP, or at the pharmacy; however, no methadone will be dispensed at the pharmacy as part of the 3-month assessment.

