4.4.5. Process measures (qualitative interviews)

The pilot study seeks to evaluate the acceptability and feasibility of having pharmacists administer methadone therapy under the supervision of OTP physicians to improve safe access to evidence-based treatment. Patient and physician or pharmacist attitudes, assessed in the pilot study, influence and ultimately determine adoption of new treatment modalities (Rieckmann, Daley et al., 2007). The patient, physician or pharmacist, and organizational attitudes are key inputs to adoption of new evidence-based approaches in healthcare settings (Damschroder et al., 2009). In the case of this pilot study, the quality of transfer of the OTP treatment to a pharmacy environment is crucial and will be adopted as a process measure. The Treatment Satisfaction Survey administered during the study to participants, pharmacists, and physicians will inform the link between treatment process and outcomes.

Additionally, at the end of the pilot study, we will conduct a qualitative interview of participating OTP's staff (e.g., physicians/medical staff, nurses, counselors), pharmacists, and study participants at the end of the study about barriers and facilitators of implementing this pilot program of pharmacy-based dispensing of methadone for the OUD maintenance care. The information will be critical to informing the future designs of the pharmacy-based dispensing and supervised methadone consumption program, including its multisite clinical trials. These interviews may be completed in-person at the OTP/pharmacy or remotely via phone or a Duke-approved teleconferencing platform.

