13.2. Secondary Outcome Measures

- **Rate of recruitment of participants into trial:** The recruitment rate will be assessed on a monthly basis until the enrollment target is reached. The recruitment rate is operationalized as the total number of participants consented in one month. The per-month proportion of consented participants reaching the pharmacy follow-up phase will also be calculated, as well as the per-month proportion of pre-screened participants that were consented. These rates will be used to estimate the speed at which a future multi-site RCT could consent, enroll, and randomize participants.
- **Treatment retention in follow-up assessments:** Retention in follow-up assessments is defined as the proportion of study assessments completed (three follow-up assessments).
- **Opioid and other substance use:** The prevalence and frequency of opioid/heroin use and other substance use over the study duration will be examined.
- **Satisfaction of participants, physicians, and pharmacists with OUD care**

Satisfaction with treatment delivery by participants will be measured using the Treatment Satisfaction Survey (adapted from Harland et al., 2005) at each visit. The proportion of visits in which participants are satisfied (score of 4 on a Likert Scale of 1-5) or very satisfied (score of 5 on a Likert Scale of 1-5) will be calculated. Pharmacist and physician satisfaction with treatment delivery will be measured using the Treatment Satisfaction Survey on a monthly basis, and a proportion of physician and pharmacist monthly ratings of satisfied or very satisfied will be calculated.

- **Participant safety, as measured by:**

- a) Any fatal or non-fatal substance use-related overdose measured by self-report.
- b) Any substance use-related ED visit or hospitalization measured by self-report.

13.3. Statistical plan and data analysis.

This is a feasibility study, and as such there are no a priori hypotheses. The main objective is to understand the feasibility regarding the study design features and operational procedures in order to inform the design of a full scale clinical trial (e.g., whether participants can be recruited in a timely fashion, whether the collaboration between the OTP and pharmacist can ensure standard methadone treatment for Opioid Use Disorder).

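### The satisfaction survey is described as a global rating whose planned summary can include baseline, so the reported percentage does not isolate satisfaction with pharmacy dispensing

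*Combined protocol and SAP*

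**What the plan says.** Section 1 (Abstract) sets the aim as the feasibility, acceptability and satisfaction of patients, OTP providers and pharmacists "with community pharmacy administration and dispensing of methadone".

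Section 4.4.4 describes the instrument: participants, pharmacists and physicians "will be asked to rate their overall satisfaction with the quality of the treatment". The items themselves are not reproduced, and no item about the pharmacy is described.

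The construct is named differently elsewhere. Objective f in section 2 speaks of "participant satisfaction with treatment delivery measured using the Treatment Satisfaction Survey". The text of section 13.2 says "Satisfaction with treatment delivery by participants will be measured using the Treatment Satisfaction Survey", under a heading that reads "Satisfaction of participants, physicians, and pharmacists with OUD care".

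On what changes for the patient, section 4.3 says that "participants will continue to receive their usual care at the OTP", giving counseling, oversight of dose orders and urine screening as examples. Section 7 confirms that nothing else in routine care alters.

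On timing, Table 1 and section 4.4.4 schedule the participant survey at baseline, at the three monthly follow-ups, and at early termination if it occurs. On analysis, section 13.2 takes the share of visits, at each visit, that are rated 4 or 5. Section 13.3 adds descriptive analysis and says that GEE models will be considered for repeated outcomes.

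Section 4.4.5 states that "the quality of transfer of the OTP treatment to a pharmacy environment is crucial and will be adopted as a process measure". It adds that the survey will inform how process and outcomes are linked, and it plans end-of-study interviews on what helped or hindered pharmacy dispensing.

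**The concern.** The question is specific to one component of care, while the instrument, as described, asks about care as a whole. A participant who is content with long-standing OTP care but dislikes collecting doses at the pharmacy could still rate 4 or 5. One who likes the pharmacy but is unhappy with OTP counseling could rate low. In neither case would the overall score show which component drove it.

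The planned summary adds a second difficulty. If ratings from every visit are pooled, some describe care before the pharmacy was involved at all.

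Satisfaction is a named aim, fills objectives f and g, and is meant to inform a later multisite randomized trial. A high percentage could be read there as evidence that patients accept pharmacy dispensing when the number does not show that directly.

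**Working it through.** **1. Is there a figure to reproduce?** No. The plan gives no target, threshold or precision for satisfaction, and the sample of up to 20 is not derived from it. The check is mainly a comparison of texts.

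**2. What is asked against what is wanted.**

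| Source | Object of satisfaction |
|---|---|
| Section 1, aim | Pharmacy administration and dispensing |
| Section 4.4.4, survey | Quality of the treatment overall |
| Section 2, objective f, and section 13.2 text | Delivery of treatment |
| Section 13.2 heading | OUD care |

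Only the first names the pharmacy. The third is closer to it than the second, but delivery can also cover counseling and prescriber contact. Observed dosing, take-home dispensing and the pharmacist's education and checks take place at the pharmacy (sections 4.4.4 and 4.5.2). Counseling, prescriber oversight and urine testing do not. A single overall score cannot be divided between these two groups.

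**3. Which ratings enter the summary.** In Table 1 the survey is marked at Visit 1 and at the three monthly follow-ups, and the first pharmacy dose is Visit 2. A completer therefore has 1 rating before pharmacy exposure and 3 after:

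- Share before exposure = 1 / (1 + 3) = 25%.
- With 20 completers and no missing data: 20 × 4 = 80 ratings, of which 20 come from Visit 1.
- For a participant with only one rating after Visit 1, the share is 1 / (1 + 1) = 50%.

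**4. Effect of pooling Visit 1.** Let *b* be the proportion satisfied at Visit 1 and *q* the proportion satisfied during the pharmacy phase. Both are assumed, since the documents give neither. With complete data:

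- Reported proportion = 0.25*b* + 0.75*q*
- Shift from *q* = 0.25(*b* − *q*)

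| *b* | *q* | Reported | Shift (points) |
|---|---|---|---|
| 1.0 | 0.6 | 0.25 + 0.45 = 70% | +10 |
| 1.0 | 0.8 | 0.25 + 0.60 = 85% | +5 |
| 0.8 | 0.6 | 0.20 + 0.45 = 65% | +5 |
| 0.8 | 0.9 | 0.20 + 0.675 = 87.5% | −2.5 |

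For *b* from 0.5 to 1.0 and *q* from 0.5 to 0.9, the shift runs from 0.25(0.5 − 0.9) = −10 points to 0.25(1.0 − 0.5) = +12.5 points. It is zero when *b* = *q*.

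**5. Effect of the global wording.** This cannot be sized from the documents. It would need the ratings of each component and the weight raters give them, and none of these is stated.

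**6. What the collected data could still show.** With other care held constant, each participant's change from Visit 1 carries indirect information about the move. Section 13.2 does not specify that contrast, and section 13.3 does not commit to a model that would estimate it.

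**The case against.** The strongest reply is that the form itself is not in the documents. Section 4.4.4 gives a short summary of an adapted instrument, and objective f and section 13.2 both call the construct treatment delivery, which is what the study changes. The form may already hold a suitable item. This stands, and it is why the fix allows for naming an existing item.

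The second reply is that the design gives some separation: a baseline rating exists, other care is unchanged, and the interviews ask about pharmacy dispensing directly. This also stands, within limits. The change from baseline is not planned, there is no control group, and stable patients may already rate near the top of the scale. The interviews complement the percentage but do not supply it.

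Third, the mixing argument is weakest for pharmacists, who deliver only the pharmacy component. That is fair, but they are still asked about the treatment overall.

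A reader might go further and infer that the survey cannot measure the aim, that most care stays at the OTP, or that this is the only quantitative evidence on acceptability. The documents support none of these. The item text is not shown. How much of care moves is a judgement, since dosing, dispensing and several pharmacist tasks do move. Enrollment among those approached, retention at the pharmacy and adherence to pharmacy visits are all quantified and bear on acceptability. Nor does section 4.4.5 say that the survey itself measures the quality of transfer.

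**Conclusion.** The point holds as a lack of specificity. As described, the rating is global and its planned summary can include a pre-pharmacy visit, so the reported percentage does not isolate satisfaction with pharmacy administration and dispensing. It is not uninformative.

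Visit 1 makes up 25% of a completer's scheduled ratings if it is counted. The resulting shift of −10 to +12.5 points rests on the assumed ranges for *b* and *q*, on complete data, and on reading section 13.2 as including baseline. The effect of the global wording has a clear mechanism but no defensible size.

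This is a descriptive secondary outcome in a pilot of up to 20. The primary outcome is unaffected. The change is still worth making before data collection, because a component that was not asked about cannot be recovered later from an overall score.

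**What to change.** - **Section 4.4.4:** add one item on satisfaction with receiving methadone doses and take-homes at the pharmacy. If the form already has such an item, name it as the scored one. Use parallel wording at Visit 1 that refers to the OTP, and parallel wording for pharmacists and physicians. Keep the overall rating as a separately reported second item.
- **Section 13.2 and objectives f and g:** compute the proportion satisfied from the pharmacy item over follow-up ratings only, and state how an early-termination rating is counted. Report Visit 1 separately, because pooling its OTP-worded item with pharmacy ratings would bring the problem back. Show within-participant change from Visit 1 descriptively.
- **Section 13.2 heading and text:** use one name for the construct.

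The cost is one more item per survey, a few lines of text and notification of the IRB. If the item already exists, only the text changes.
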